## 2.3 Objectives and Hypotheses

#### 2.3.1 Primary objectives

To evaluate the safety and tolerability of the multi-dose Lagricel® Ofteno formulation manufactured by Sophia Laboratories S.A. of C.V. on the ocular surface of clinically healthy subjects.

#### 2.3.2 Specific objectives

- Compare the safety of the Lagricel® Ofteno multi-dose formulation against Lagricel®
   Ofteno unit doses manufactured by Sophia Laboratories S.A. of C.V. through the incidence
   of AD.
- Compare the tolerability of the Lagricel® Ofteno multi-dose formulation against Lagricel®
   Ofteno unit-dose manufactured by Sophia Laboratories S.A. of C.V. using the ICO score.

#### 2.3.3 Secondary objectives

- Compare the safety of the Lagricel® Ofteno multi-dose formulation against Lagricel® Ofteno unit doses manufactured by Sophia Laboratories S.A. of C.V. through changes in CV.
- Compare the safety of the Lagricel® Ofteno multi-dose formulation against Lagricel® Ofteno unit doses manufactured by Sophia Laboratories S.A. of C.V. by changes of corneal and conjunctival staining with lysamine green.
- Compare the safety of the Lagricel® Ofteno multi-dose formulation against Lagricel® Ofteno unit doses manufactured by Sophia Laboratories S.A. of C.V. by changes in corneal and conjunctival staining with fluorescein.
- Compare the safety of the Lagricel® Ofteno multi-dose formulation against Lagricel® Ofteno unit doses manufactured by Sophia Laboratories S.A. of C.V. by changes in conjunctival hyperemia.
- Compare the safety of the Lagricel® Ofteno multi-dose formulation against Lagricel® Ofteno unit doses manufactured by Sophia Laboratories S.A. of C.V. through the incidence of chemosis

#### 2.3.4 Hypotheses

H0 = Lagricel® Ofteno multi-dose ophthalmic solution has a safety and tolerability profile similar to Lagricel® Ofteno single-dose in healthy subjects.

H1 = Lagricel® Ofteno multi-dose ophthalmic solution has a different safety and tolerability profile than Lagricel® Ofteno single-dose in healthy subjects

## 2.4 Study design

#### 2.4.1 Description overall design

Phase I, single-center, controlled, parallel-group, open-label, randomized clinical trial.

#### 2.4.2 Justification of the study design

The study design (clinical trial) is considered the highest quality standard in data when looking to explore the effect of an intervention. The drug development phase (phase I) corresponds to the objective of the study, which is to evaluate safety and tolerability, so the intervention time is short and the required sample size is smaller than that of a clinical efficacy trial. The presence of parallel groups allows comparison between the intervention groups on the outcome variables. Blinding was not considered for this study due to the characteristics of both investigational products.

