#### center.

#### Example:

## 2.6 Investigational product

#### 2.6.1 Managed Products

#### 2.6.1.1 Investigational Product

- Generic name: Sodium Hyaluronate
- Distinctive name: Lagricel® Ofteno multi-dose (PRO-037)
- Active principles: Sodium Hyaluronate 0.4%.
- Excipients: sodium chloride, monobasic sodium phosphate monohydrate, anhydrous dibasic sodium phosphate, water for the manufacture of injections.
- Pharmaceutical form: Ophthalmic solution
- Presentation: multi-dose dropper bottle.
- Prepared by: Sophia Laboratories S.A. of C.V.
- Description of the solution: clear solution, free of visible particles.
- Description of the container: White bottle with a capacity of 10 mL, made of low-density polyethylene.

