#### 2.6.1.2 Reference product

- Generic name: Sodium Hyaluronate
- Distinctive name: Lagricel® Ofteno unit dose
- Active principles: Sodium Hyaluronate 0.4%.
- Excipients: sodium chloride, monobasic sodium phosphate monohydrate, anhydrous dibasic sodium phosphate, water for the manufacture of injections.
- Pharmaceutical form: Ophthalmic solution
- Presentation: Single dose vial.
- Prepared by: Sophia Laboratories S.A. of C.V.
- Description of the solution: clear solution, free of visible particles.
- Description of the container: transparent vial with a capacity of 0.5mL.

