# 7. Study methods and procedures

#### 7.1 From the research center

The present study will be carried out in a research center previously evaluated by the sponsor. This center will be an institution or establishment where health research is carried out that complies with current regulations.

The research center will be responsible for forming a multidisciplinary research team to execute the clinical study according to protocol. It is their prerogative to design the organization and select the personnel who will carry out the functions. However, it is the sponsor's need for the Principal Investigator (PI) to be an ophthalmology specialist.

Any person who is appointed, under their responsibility, a part of the study follow-up (co-investigator, sub-investigator, nurse, etc.) or a specific role for participation in the study (pharmacist, administrative assistant, study coordinator, etc.) It must appear in the "Delegation of Responsibilities".

The competence and training of any person who has direct participation in the study activities must be verified before carrying out any activity related to the protocol. The foregoing must be recorded and the documents that constitute evidence of this competence and / or training must be kept in the master file of the study. The competence and training of the personnel who have functions in the study, both at the central level and in the study centers is the responsibility of the sponsor.

The sponsor must ensure that all the personnel of the study centers participating in the study are adequately trained on the study (research protocol, investigator's manual, amendments, standard operating procedures, etc.) and on the Good Clinical Practices of the ICH, before the start of your participation in it. Training must be recorded in writing and those records must be filed in the study master file.

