### 7.2 Randomization and Blinding

Subject randomization will be carried out using a computerized assignment system. After signing the FCI, the patient will receive a patient number with which all their information will be coded pseudo anonymously during collection and completely anonymized during analysis.

The generation will be carried out by a third party, authorized by Sophia Laboratories S.A. of C.V., through its electronic system. The information for this third party will be in the file.

Although it is an open study, the secondary container will be masked.

PIs will be identified by means of labels in accordance with current and applicable regulations, they must contain at least:

- Name, address and telephone number of the sponsor.
- Pharmaceutical form and route of administration.
- Lot Number.
- Legend "Exclusively for clinical studies"
- Date of Expiry.

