#### 7.3.3.4 Corneal and conjunctival fluorescein staining

A drop of topical anesthetic will be instilled in the conjunctival cul-de-sac, then a second drop will be applied to the tip of the fluorescein strip allowing it to settle on the strip for 5 seconds to elute the dye, shaking off the excess at the end. A small contact of the strip with the conjunctiva is made in the temporal cul-de-sac, while the patient looks up, without damaging the conjunctiva. It will be graded according to the Oxford scale. [42]

The IP will record in the file and the FERC the grade awarded for fluorescein staining of OD and OS respectively.

Management as AE: corneal stains that are equal to or greater than grade III will be considered as AE.

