- -Delivery of the PI and start of intervention: It refers to the delivery of the PI to the study patient, by the research center. See
- -Evaluation of EA: See 7.4.3.1
- -Delivery of patient material and filling instructions: It refers to the delivery by the IP to the subject of the subject's diary, identification card and calendar, improving adherence. The assigned personnel will carry out a previous training to the subject, on the filling of the diary.

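### Nothing in the protocol keeps the day-8 grader of staining, hyperemia and chemosis unaware of arm, and the reason given for not blinding covers subjects but not the grader

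*Combined protocol and SAP*

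**What the plan says.** Section 2.4.1 describes the trial as "Phase I, single-center, controlled, parallel-group, open-label, randomized clinical trial". Section 2.4.2 gives the only reason for the absence of masking: "Blinding was not considered for this study due to the characteristics of both investigational products".

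The visible difference is the primary container. The test product comes in a "White bottle with a capacity of 10 mL, made of low-density polyethylene" (2.6.1.1) and the reference in a "transparent vial with a capacity of 0.5mL" (2.6.1.2). Section 2.2.4 says the formulations are identical.

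Two masking steps remain. Section 7.2 states: "Although it is an open study, the secondary container will be masked". Section 10.1.1 blinds the staff who analyse the data. Neither concerns the person who examines the eye.

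On grading, 7.3.3.4 says: "The IP will record in the file and the FERC the grade awarded for fluorescein staining of OD and OS respectively". Section 7.3.3.5 assigns the recording of the second stain in the same way. Hyperemia is graded on the Efron scale by direct observation (7.3.3.6), and chemosis is judged present or absent by the evaluator (7.3.3.7).

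On product hand-out, 7.4.1.1 says: "It refers to the delivery of the PI to the study patient, by the research center". It does not name the person.

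**The concern.** A difference in container is a sound reason for not masking the subject, who handles it four times a day. It is not a reason for leaving the examiner unmasked, because grading the cornea and conjunctiva does not require seeing the container. The justification in 2.4.2 does not separate the two roles.

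What is at stake is observer bias in outcomes that rest on visual judgement. The decision rule in 10.1.5 adds some weight. The product is accepted if the arms do not differ, clinically or statistically, on the primary outcomes. An examiner who knows the arm, and knows that the formulations are identical, might grade the arms alike. That direction is plausible, but the documents do not show it. Blinding the analysts cannot correct a grade already recorded.

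**Working it through.** The plan gives no figure on this point, so the check is mainly a comparison of sections.

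**1. Which outcomes depend on the observer (7.3.2, 7.3.3)**

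| Outcome | How it is judged | Becomes an adverse event when |
|---|---|---|
| Fluorescein staining (secondary) | Oxford scale, slit lamp | corneal grade III or above |
| Lissamine green staining (secondary) | Oxford scale, slit lamp | corneal grade III or above |
| Conjunctival hyperemia (secondary) | Efron scale, direct observation | grade 3 or above |
| Chemosis (secondary) | present/absent, slit beam | present |
| Best corrected visual acuity (secondary) | Snellen chart | loss of more than 2 lines |
| ICO (primary) | completed by the subject | not by score alone |

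The first four of the five secondary outcomes are examiner judgements of signs. Through the last column they can reach the primary adverse-event outcome. Section 7.3.3.1 also leaves it to the principal investigator which examination findings are entered as adverse events.

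**2. Whether any section masks the grader**

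- 2.4.1 and 2.4.2: open design; only the products are discussed.
- 7.2: outer packaging only.
- 7.3.3.4 to 7.3.3.7: grading methods, with no condition on knowledge of arm.
- 10.1.1: analysts only.

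No such requirement appears.

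**3. Whether the visit structure would allow it**

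- 7.4.1.1: at baseline, stains and examination are listed before assignment, so baseline grades come before allocation.
- 7.4.1.2: at the final visit, stains and examination are listed before diary review, adherence and product return. Section 7.4.1 calls the order a suggestion.
- 7.1: the site must form a multidisciplinary team and may give someone "a specific role for participation in the study (pharmacist, administrative assistant, study coordinator, etc"; these are examples.
- 7.4.1.1: delivery is left to the research center, and assigned personnel train the subject on the diary.
- 6.5: the principal investigator questions the subject about product use. This route to knowing the arm would need to move.

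**4. Scale**

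With 17 subjects per arm (10.2.1), one subject reclassified moves an arm's adverse-event incidence by 1/17 = 5.9 percentage points. With 14 per arm, the figure before the loss allowance in 10.2.2, it is 1/14 = 7.1 points. This is the step size of a proportion at that sample size. Any single event from any cause produces it, so it does not measure bias.

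**The case against.** The strongest reply is that this is a declared design choice in a short phase I comparison of identical formulations, and that the visit order already does much of the work. Baseline grades come before assignment, and at the final visit grading is listed before the diary and containers appear. What remains is mainly knowledge carried over from day 1 or disclosure by the subject. This stands, and it limits the exposure. But the order is only suggested, and nothing prevents the same person from assigning, dispensing and later grading.

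A second reply is that the primary outcomes rest largely on subjects. The ICO is self-completed. The expected adverse events in 7.3.3.1 are mostly sensations, and burning and pruritus were the commonest ocular events in the reference study (10.2.2). Signs count as adverse events only at set thresholds, in healthy subjects after 7 days, and the documents give no rate for them. This also stands.

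Four stronger readings are tempting, and the documents do not support them:

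- *That the grades are made with knowledge of the arm.* No section says so. Several refer simply to the evaluator, and a site could already separate the roles. What can be said is that masking is not required.
- *That one reclassified subject, at 5.9 points, exceeds the 5% margin and could overturn the result.* The margin appears only in the sample-size section (10.2.2), and the decision rule in 10.1.5 does not use it.
- *That a named coordinator or pharmacist is already in place.* Section 7.1 lists possible roles and leaves staffing to the site.
- *That causality and all diary review should also be masked or moved.* Section 8.4 has the investigator verify adverse events partly from the diary, and 8.4.1 requires product details in the record. Masking those steps would conflict with both.

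**Conclusion.** The point holds as a limited one. The protocol does not require the day-8 grader to be unaware of arm, and the reason in 2.4.2 does not explain why. Four of the five secondary outcomes are affected, and through the thresholds part of the primary adverse-event outcome may be too. The size and direction of any bias cannot be derived from the documents, and threshold-level signs may be uncommon in healthy subjects.

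Masking the grader would reduce this source of bias without removing it. Symptom reports and the ICO would still come from subjects who know their product. If an adverse event is handled before day 8, the investigator may learn the arm through the record that 8.4.1 requires.

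The conclusion assumes that the site's team includes at least one person besides the grader who can handle product. The team required by 7.1 makes that likely, but the sponsor should confirm it.

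**What to change.** - **7.2 and 7.4.1:** state that a team member other than the day-8 grader makes the assignment, dispenses the product and collects it in its masked secondary container.
- **6.5:** give adherence questioning to that same person.
- **7.4.1.2:** make the present order binding for this purpose, so that staining, hyperemia and chemosis are graded and recorded before diary review and product return.
- **Subject instructions:** ask subjects not to show or describe the container before grading.
- **8.4 and 8.4.1:** leave unchanged. Adverse-event verification, diary review for adverse events, causality and product details stay with the investigator, after the grades are recorded.

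If the sponsor judges this infeasible, 2.4.2 should say why for the grader specifically.

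Cost: wording edits and a division of tasks within the existing team, with no change to sample size, visits or assessments. The downside is that some subjects may still disclose their product. Label: cheap improvement.

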#### 2.4.3 Expected duration

The total duration of the study, from the first visit of the first patient to the preparation of the final report, is estimated to be 5 months.

The planned recruitment period is 3 months. Considering that the proposed sample is 34 subjects, the total average recruitment rate during the study should be no less than 0.37 subjects per day.

The approximate duration of each subject in the study is 10 days.

## 2.5 Study population

#### 2.5.1 Elegibility criteria

#### 2.5.1.1 Inclusion criteria

- Be clinically healthy
- Have the ability to voluntarily grant your signed informed consent
- Be able and willing to comply with the scheduled visits, treatment plan and other study procedures
- Be between 18 to 45 years old.
- Women of childbearing age must ensure the continuation (started ≥ 30 days prior to signing the FCI) of use of a hormonal contraceptive method or intrauterine device (IUD) during the study period
- Have a best corrected visual acuity of 20/30 or better in both eyes.
- Have vital signs within normal parameters.
- Have an intraocular pressure ≥10 and ≤ 21 mmHg

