#### 2.4.2 Known potential benefits

As they are healthy subjects, no potential benefits for the subjects are expected. An improvement in eye comfort may occur, however, it may not be significant.

The benefits of the study will be to document the safety profile of Lagricel® Ofteno multi-dose.

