#### 2.5.1.2 Exclusion Criteria

- Be a user of topical ophthalmic products of any kind.
- Being a user of medicines, or herbal products, by any other route of administration.
- In the case of women: be pregnant, breastfeeding or planning to become pregnant within the study period.
- Have participated in clinical research studies 90 days prior to inclusion in the present study.
- Have previously participated in this same study.
- Be a user of contact lenses and cannot suspend their use during the study.
- They cannot follow the lifestyle considerations described in section 5.3.
- Having started the use of hormonal contraceptives or IUDs, 30 days prior to inclusion in the present study.
- Have a history of any chronic degenerative disease.
- Present inflammatory or infectious disease, active at the time of entry to the study.
- Present unresolved injuries or trauma at the time of study entry.
- Have a history of any type of eye surgery.
- Having undergone surgical procedures, not ophthalmological, in the last 3 months.
- Being or having an immediate family member (for example: spouse, parent / legal guardian, brother or child) who is part of the research site staff or the sponsor directly participating in this study.

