#### 7.4.1.1 Basal visit

- -FCI Signature: refers to the signature of the written informed consent document. Without obtaining informed consent, it is not possible to perform any of the study procedures
- -Clinical history: refers to the technical, clinical and legal document in which the subject's health conditions, medical acts and other procedures performed on the subject are chronologically recorded. It includes anthropometric measurements, anamnesis, comprehensive ophthalmological examination that allows discerning the eligibility of the patient, that is, evaluation of both eyes of ocular attachments, slit lamp examination of the ocular surface and anterior segment, and funduscopy. If the subject is taken from the established population base of the study center, the existing clinical history may be used, only an update being required.
- -Evaluation of concomitant medications: refers to the questioning by the PI of the subject, inquiring about the use of medications.
- Pregnancy test in urine: It refers to the realization of a rapid pregnancy test in all women of childbearing age who wish to enter the study. By childbearing age we understand women who have had their menarche and have not had their menopause. Menopause is defined as 12 months from the last menstruation in women over 40 years of age, or who have undergone a bilateral hysterectomy or oophorectomy. Women of childbearing potential with contraceptive methods including bilateral tubal obstruction should undergo a pregnancy test. This test will be performed by the IP or the designated team person in accordance with the instructions of the device provided by the sponsor
- -Vital signs: refers to the taking of heart rate, respiratory rate, systemic blood pressure and temperature. This information must be contained in the patient's medical record and the progress notes of the patient's clinical record.
- -MAVC: See 7.4.3.2
- -ICO: See 7.4.3.2
- Ocular surface stains: See 7.4.3.4 and 7.4.3.5
- Ophthalmological evaluation: See 7.4.3.1
- -Eligibility criteria: refers to the review by the PI, where it verifies that the subject can be included in the study by meeting the inclusion criteria and not meeting the exclusion criteria. See 5.1

- -Assignment of PI: It refers to determining the intervention that the patient will follow during the study. It will be carried out according to section 7.3. This assignment will be made at the baseline visit (day 1).

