#### 10.2.2 Justification of the sample calculation

Although there are no references on the calculation of the sample size in phase I studies, it was considered pertinent to perform it according to the safety results of a phase I study, carried out with three ocular lubricants (Humylub Ofteno® PF, Xyel® Ofteno and Systane® Ultra). [53]

The reference study was a single-center, randomized, 1: 1: 1, parallel group, blinded clinical trial. In total, 30 ophthalmologically and clinically healthy subjects were enrolled and included in the safety analyzes.

PRO-037 (Lagricel® Ofteno, multi-dose) is expected to be not inferior to its comparator (Lagricel® Ofteno, single-dose), based on the following working hypotheses:

$$H_0: \varepsilon > \delta$$

$$H_0: \varepsilon \leq \delta$$

Where  $\mu A - \mu B = \epsilon$ , the true difference of the means between the test treatment (Lagricel® Ofteno, multi-dose) and the active control (Lagricel® Ofteno unit-dose). Where  $\delta$  is the margin of non-inferiority, and the relationship between the sample sizes of the two groups is given by:

$$k = \frac{n_A}{n_B}$$

The calculations were made using the equation for two proportions, considering a power of 80% ( $\beta$ ), a significance level of 0.05 ( $\alpha$ ) and a non-inferiority margin ( $\delta$ ) of 5%. [54]

$$n_B = (\frac{p_A(1-p_A)}{k} + p_B(1-p_B))(\frac{z_{1-\alpha} + z_{1-\beta}}{k})^2$$

$$p_A - p_B - \delta$$

In the reference study, after 10 days of treatment (1 drop / 4 times a day), 28 AE were reported in 14 subjects out of a total of 30 subjects exposed to any of the three interventions (46.67%). Without observing statistical differences in the incidence of AE between the three treatment arms (p = 0.788), 19 of the AE were ocular, where burning was the most common, followed by pruritus. Other ocular AE reported were discharge, SCE, and dry eye sensation.

The percentage of ocular AE reported in the study was considered, with respect to the total AE for the three treatments. As it is an ocular lubricant, a similar proportion of ocular AE is expected in ophthalmologically and clinically healthy subjects (50%).

The calculated sample was 56 eyes (28 eyes / arm; 14 subjects / arm), increasing the calculation by 20% considering possible losses, 17 subjects / arm (both eyes) are estimated.

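### The entry criteria set no ocular-surface limit, so an eye that already meets one of the plan's adverse-event definitions can be randomised unless the investigator chooses to exclude it

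*Combined protocol and SAP*

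**What the plan says.** **Entry.** Section 2.5.1.1 (repeated in the synopsis) requires the volunteer to "Be clinically healthy", without defining it. Two ocular limits carry numbers: "Have a best corrected visual acuity of 20/30 or better in both eyes" and "Have an intraocular pressure ≥10 and ≤ 21 mmHg". The exclusions in section 2.5.1.2 that bear on the eye include "Be a user of topical ophthalmic products of any kind", past eye surgery, contact lenses that cannot be given up, unresolved injury, and "Present inflammatory or infectious disease, active at the time of entry to the study". No criterion names dry eye, an Oxford or Efron grade, chemosis or an ICO score.

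**Baseline visit.** Section 7.4.1.1 asks for an ophthalmological examination from which eligibility can be judged, with no threshold. It lists the ICO, the stains and the eye evaluation ahead of the step in which the investigator "verifies that the subject can be included in the study by meeting the inclusion criteria and not meeting the exclusion criteria". Section 7.4.1 says that the listed order is the suggested one. The table in section 1.2 also places staining before eligibility, but places the ICO after both eligibility and product allocation.

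**Adverse events.** Sections 7.3.3.4 to 7.3.3.7 treat corneal staining of grade III or more, hyperaemia of grade 3 or more, and any chemosis as adverse events. None of them refers to the baseline finding.

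**Planning and conclusion.** Section 10.2.2 takes its rate from a study in ophthalmologically and clinically healthy volunteers and states that "a similar proportion of ocular AE is expected in ophthalmologically and clinically healthy subjects (50"%). Section 10.1.5 declares the product safe and effective if no primary outcome differs from the comparator. Section 2.4.2 says of comfort: "An improvement in eye comfort may occur, however, it may not be significant".

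**The concern.** The objective is safety and tolerability on the ocular surface of healthy people, yet the ocular surface is what the written criteria leave open. Excluding users of eye products removes treated dry eye but not untreated dry eye. The word healthy does not close the gap, because section 2.6 itself speaks of dry-eye symptoms in otherwise healthy people.

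Three things are at stake:

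- A subject may enter with an eye that already satisfies an adverse-event definition, and adverse-event incidence is a primary outcome.
- Such subjects add variation to small arms. Because section 10.1.5 reads an absence of difference as success, added variation works in favour of that conclusion.
- Whether such a subject enters depends on one investigator's judgement, without a written standard that a monitor could check.

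**Working it through.** **1. Do the criteria admit such a subject?** Take a volunteer aged 18 to 45 with untreated ocular-surface signs, acuity 20/30 or better, pressure of 10 to 21 mmHg, no eye products and no eye surgery.

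| Signs at baseline | Table 2 normal value | Written entry limit | Adverse-event rule |
|---|---|---|---|
| Corneal staining, either dye | 0 | none | grade III or more |
| Hyperaemia (Efron) | Normal | none | grade 3 or more |
| Chemosis | Absent | none | present |
| ICO | none given (NA) | none | score alone is not an adverse event |

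Only the undefined word healthy, the general exclusion of active inflammatory disease and the examination in section 7.4.1.1 could stop this subject. All three need interpretation.

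**2. The plan's own sample figure.** Section 10.2.2 gives 28 eyes (14 subjects) per arm, and 14 x 1.2 = 16.8, hence 17. With 50% in both arms, a 5-point margin, one-sided 0.05 and 80% power, the section's formula gives 1,237 per arm, so the 28 does not reproduce. That is a separate problem. For the present point, raising the rate from 50% to an assumed 65% changes the formula's answer only from 1,237 to 1,126. The mismatch in population therefore matters for comparability and event counting, not for the size calculation.

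**3. Effect on adverse-event incidence.** Events are reported as numbers of subjects. One subject counted only because of a sign present at entry adds 1/17 = 5.9 percentage points to that arm, and a two-subject imbalance adds 2/17 = 11.8. The margin used for planning is 5 points. These are upper values, since such a subject may also have a genuine event.

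**4. Chance imbalance.** The documents give no prevalence for ages 18 to 45. Section 2.1 cites 5 to 50% in symptom-based studies that are not specific to that age range. Let q be the assumed share of entrants with untreated ocular-surface symptoms or signs, and let the count in each arm be Binomial(17, q), independently.

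| q | Expected among 34 | Arms differ by 2 or more | Arms differ by 3 or more |
|---|---|---|---|
| 5% | 1.7 | 21% | 5% |
| 10% | 3.4 | 38% | 15% |
| 20% | 6.8 | 52% | 28% |

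At 5%, at least one such subject enters in 1 - 0.95^34 = 83% of trials. The share already at an adverse-event threshold would be some part of q.

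**5. Effect on the ICO.** If these subjects score 30 points higher (assumed), an imbalance of two moves the difference in means by 2 x 30/17 = 3.5 points, and of three by 3 x 30/17 = 5.3. At an assumed 10 points, the shifts are 1.2 and 1.8. The planned test is Mann-Whitney, which uses ranks. Simulating 17 per arm with no treatment effect, and extra subjects in one arm scoring above everyone else, gives a rejection rate of about 7% with two extra and 10 to 11% with three, against 5% with none. Averaged over randomisation at q = 5%, 10% or 20%, the rate stays at about 5%.

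**The case against.** The strongest reply is that the protocol is not silent. The investigator must be an ophthalmologist (section 7.1), the baseline examination exists to judge eligibility, and section 2.1 gives inflammation a role in dry eye, so the exclusion of active inflammatory disease could be used against a marked case. This stands as far as it goes: exclusion is possible. It is discretionary, because no threshold is written.

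A reader might infer that the gap biases the comparison or inflates false positives. The documents do not support that. Allocation is randomised, and averaged over randomisation the rank test keeps its level. A reader might also infer that a lubricating benefit hides irritation in the test arm alone. Section 2.2.4 states that the formulations are identical, and both arms have the same dosing, so any such benefit is expected in both. It can dull the study's ability to see irritation, but it does not favour one arm.

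Nor does every outcome carry the baseline state through to day 8. Section 7.3.2 defines the staining and hyperaemia outcomes as changes, so baseline is at least partly accounted for there. The ICO is listed as a day-8 score with no stated adjustment.

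Section 8.2 describes adverse events partly as new or worsening conditions, which might keep a pre-existing sign out of the count. The sign-specific rules do not say so, and Table 2 also lists the baseline visit among the times at which events are counted.

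Finally, it is tempting to say that the ICO is always known before eligibility is decided. Section 1.2 lists it after allocation, contrary to section 7.4.1.1.

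**Conclusion.** The point holds as a gap in the written criteria. An untreated subject with ocular-surface signs, including an eye already at an adverse-event threshold, can be randomised, and only investigator discretion prevents it. The population that the criteria describe is wider than the one assumed in section 10.2.2.

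The consequence is chance imbalance and reduced sensitivity at 17 per arm, not systematic bias. The 5.9 points per subject follow from the arm size alone. The imbalance probabilities rest on assumed shares of 5 to 20%, and the ICO shifts on assumed gaps of 10 to 30 points. The documents supply neither, and they give no standard deviation for the ICO. The change is worth making because it is cheap and protects a primary safety outcome, not because the trial would otherwise be invalid.

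**What to change.** - **Eligibility.** Replace the health criterion with *clinically and ophthalmologically healthy in both eyes*. Define this at the existing baseline examination as no known dry-eye diagnosis and no eye already meeting the plan's own adverse-event thresholds for staining, hyperaemia or chemosis. Apply it at the existing eligibility check, before allocation.
- **ICO.** Table 2 gives no normal value, and the sign-based line would still admit a symptomatic subject without marked signs. Handle this in the analysis by prespecifying change from baseline or adjustment for baseline ICO.
- **Order.** Reconcile section 1.2 with section 7.4.1.1 so that baseline ICO is recorded before allocation.

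The cost is an amendment with one eligibility line, one analysis sentence and one table correction. The measurements are already planned, so no procedure is added. There will be some further screening failures, which cannot be quantified from the documents, against a required recruitment rate of 0.37 subjects per day, and the population will be slightly narrower. Requiring Table 2's full normal values would be stricter and would lose more volunteers. The adverse-event thresholds are the minimum that closes the gap.
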